5.0 CONE BEAM COMPUTED TOMOGRAPHY

Cone-Beam Computed Tomography (CBCT) will be used in this trial to obtain a 3-dimensional database of each participant's anatomy from the volumetric tomography. Axial, sagittal, and cross-images will be reconstructed to measure tooth socket volume. CBCT imaging is used in state-of-the-art dentistry to aid treatment planning of complex implant cases and is considered best practice in dental imaging. The CBCT produces a highly accurate scan of the head and neck. The image can then be visualized as a virtual reproduction of the jaw that is accurate to within a tenth of a millimeter (0.10mm). A CBCT scan allows the dental surgeon to view the anatomy in many different planes and

provides precise knowledge of the disposition of anatomical structures. These views enable the dental surgeon to select an implant with the most appropriate configurations to fit the anatomy of each individual patient.

Participants in this study will have 2 CBCT scans made; the first will aid in the initial treatment planning, the second scan will be used to assess bony healing of the grafted sites prior to implant placement. The images will be captured using I-Cat, Cone Beam CAT scanning equipment, manufactured by Imaging Sciences and designed especially for imaging the skull in the dental setting. CBCT scans are acquired through a series of rapid pulses in a single pass, exposing the patient to radiation for the equivalent of 3 seconds per image. These scans compare favorably to hospital-based CT scans of the head and neck area where exposure is 30 times greater.

A Cone Beam Computed Tomography (CBCT) scan will be made at baseline (immediately post-grafting), and at 7 weeks after the grafting.

6.0 TISSUE BIOPSY AND SURGICAL PLACEMENT OF IMPLANTS

6.1 Patient Preparation and Surgical Implant Placement

Prior to implant surgery the subjects will be given a loading dose of antibiotics based on their medical history and concomitant medications. Local anesthesia will be achieved in the region by regional block or local infiltration. Conscious sedation may be added at the surgeon's discretion to help manage a patient's anxiety. The facial area will be scrubbed with 2% Chlorhexidine soap and the oral cavity disinfected by rinsing for 1 minute with a 0.12% chlorhexidine gluconate antimicrobial oral rinse prior to the procedure.

Once the treatment areas are sufficiently anesthetized a crestal incision will be made and full-thickness flaps will be raised. With the aid of a surgical guide, the proposed implant sites will be identified; measurements of the alveolar ridge will be captured, using a UNC-15 periodontal probe and recorded on the implant surgery CRF.

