2.3 Hypotheses and Specific Aims

The trial will test two hypotheses:

Hypothesis-1: Grafting with Bone Allograft is an efficacious method of enhancing the development of new bone fill in extraction sockets.

Hypothesis-2: Bone Allograft/Amniotic allograft will aid osseous healing and will preserve alveolar ridge dimensions of extraction sockets more effectively than extraction sites grafted with Bone Allograft alone.

Specific Aims

- 1: Compare the efficacy of bone grafting with and without enrichment with amnion.
- 2: Compare alveolar ridge dimensions between groups after 7 weeks of post-extraction healing.
- 3: Compare soft tissue healing between groups at week-1, week-2, week-4 and after 7 weeks of post-extraction healing.

- 4: Assess quantitative bone fill between groups after 7 weeks of post-extraction healing
- 5: Compare qualitative bone fill between groups after 7 weeks of post-extraction healing.
- 6: Assess and compare the relationship of osseous healing and implant stability at insertion across groups after 8 weeks of post-extraction healing.
- 7: Compare implant stability between groups at 12 months and 24 months post-restoration.
- 8: Assess changes in longitudinal crestal bone level between groups at 12 and 24 months after permanent prosthetic attachment.

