4.5 Surgical Extractions

All surgeries will be performed by qualified clinicians/investigators in an appropriately equipped surgical operatory located in the Periodontal Clinic at UAB School of Dentistry.

Prior to extraction surgery, participants will be given a loading dose of antibiotics based on their medical history and concomitant medications. A suggested prophylactic regimen follows:

2 gm of Amoxicillin 1 hour prior to the procedure followed by 500 mg (TID) for 7 days
Patients with reported allergy to Amoxicillin:
600mg Clindamycin 1 hour prior to the procedure followed by 300 mg (TID) for 7 days

The facial area will be scrubbed with 2% Clorhexidine soap and the oral cavity disinfected by rinsing for 1 minute with a 0.12% chlorhexidine gluconate antimicrobial oral rinse. Prior to extractions clinical photographs will be taken from the buccal and occlusal aspects. Photographs will be taken in a 1:1 ratio using a Nikon D-7000.

After preparation and isolation of the surgical area, anesthesia will be achieved in the region by regional block or local infiltration. Conscious sedation may be added at the surgeon's discretion to help manage patient anxiety.

The teeth will be extracted as atraumatically as possible, without raising a flap, utilizing periotomes, luxators and the Easy Extrac system. In both groups, the integrity of the remaining socket walls will be assessed and measurements recorded on the surgical CRF. The sockets will be debrided and a bleeding surface created by decorticate the socket walls with either a curette or a surgical round burr.

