4.7 Surgical Extraction Data Collection

The following data points will be collected and recorded on the surgical CRF: A description of the integrity of each of the socket walls will be recorded as follows.

4.7.1 Measurements of the Mesio-distal distance and the buco-lingual distance of the socket walls.

4.7.2 Measurements of dehiscence and fenestration defects made with a UNC-15 periodontal probe in relation to the adjacent socket crest and rounded up to the nearest millimeter.

4.7.3 Wound Measurements – Mesio-distal distance and bucco-lingual distance of the soft tissue wound margins after suturing made with a UNC-15 periodontal probe and rounded to the nearest millimeter.

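### Ridge preservation has no defined change endpoint: the one named ridge measurement is a week-8 open-flap probe reading without a matching baseline, and the paired CBCT scans are not assigned to it

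*Combined protocol and SAP*

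**What the plan says.** **The claim.** Section 2.3, Hypothesis-2, states that the combined graft "will preserve alveolar ridge dimensions of extraction sockets more effectively than extraction sites grafted with Bone Allograft alone". Aim 2 in the same section is to "Compare alveolar ridge dimensions between groups after 7 weeks of post-extraction healing".

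**At extraction.** Section 4.5: "The teeth will be extracted as atraumatically as possible, without raising a flap". Item 4.7.1 then records "Measurements of the Mesio-distal distance and the buco-lingual distance of the socket walls". No instrument, level or rounding rule is given for that item.

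**At week 8.** Section 6.1: "a crestal incision will be made and full-thickness flaps will be raised", after which "measurements of the alveolar ridge will be captured, using a UNC-15 periodontal probe and recorded on the implant surgery CRF". No dimension, level, landmark or rounding rule is given.

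**On CBCT.** Section 5.0 schedules scans immediately after grafting and at 7 weeks, states an accuracy of 0.10 mm, and gives their use: "Axial, sagittal, and cross-images will be reconstructed to measure tooth socket volume". Section 13.1 assigns CBCT to bone fill. The synopsis outcome list includes radiographic analysis of changes in osseous architecture, but names no ridge variable.

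**On analysis.** Section 13.4 plans two-sided t or Wilcoxon tests between groups at alpha 0.05, and paired tests of change in bone growth. Ridge width and height do not appear. Section 3.1 sets 10 participants per group, with sites among maxillary anterior teeth and premolars of both jaws. Section 4.2 stratifies by smoking only.

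**On sites that drop out.** Under 4.9 the investigator reviews the CBCT scans before deciding whether implants can be placed. Under 11.1 a site whose ridge stays too narrow for an implant is re-grafted, if the patient accepts, and leaves the study results.

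**The concern.** Preservation is a statement about change, or at least about where a ridge ends up given where it began. The protocol collects one reading that it calls a ridge measurement, late and under conditions that differ from those at extraction. It does not say that the one paired, same-method data source, CBCT, will be used for the ridge.

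Three things are at stake. First, the loss of ridge in each arm cannot be calculated. Second, the comparison between arms loses the precision that a baseline would bring, in a trial of 20 people whose sites differ in natural ridge width. Third, the week-8 reading may be absent for just those sites where the ridge did worst. If one graft leaves more narrow ridges than the other, the arms compared at week 8 are no longer the arms that were randomised.

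**Working it through.** The plan gives no effect size, SD or power, so there is no figure to reproduce. The check has two parts.

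**1. What is measured, when and how**

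| Source | Time | Quantity named | Conditions | Matched pair? |
|---|---|---|---|---|
| 4.7.1 | Extraction | Socket-wall distances | No flap | No |
| 6.1 | Week 8 | Alveolar ridge, dimension not stated | Full-thickness flaps, UNC-15 probe | No |
| 5.0, 13.1 | Post-grafting and week 7 | Socket volume, bone fill | CBCT, same method twice | Yes, but not for the ridge |

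No row gives a ridge dimension at two times by one method. The only row at Aim 2's time point is CBCT, and it names other quantities.

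**2. What the missing baseline costs**

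Inputs: n = 10 per group (3.1) and two-sided alpha 0.05 (13.4). Assumptions, because the documents give no figures: 80% power, SD 1 mm, one value per participant, no loss, and a correlation rho between baseline and follow-up of 0 to 0.9.

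Detectable standardised difference, follow-up value only:
- Normal approximation: (1.960 + 0.842) × √(2/10) = 1.25 SD.
- t test: noncentral t with 18 degrees of freedom and noncentrality d × √(10/2); power reaches 0.80 at d = 1.325 SD.

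In millimetres the t-test figure is 0.66, 1.32, 1.99 or 2.65 for an SD of 0.5, 1, 1.5 or 2 mm.

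With a matched baseline, the SD is multiplied by √(1 − rho²) for baseline adjustment (ANCOVA), or by √(2(1 − rho)) for a simple change score. The one degree of freedom that ANCOVA spends on the baseline is ignored here. At SD 1 mm:

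| rho | Follow-up only (mm) | Change score (mm) | ANCOVA (mm) |
|---|---|---|---|
| 0 | 1.32 | 1.87 | 1.32 |
| 0.3 | 1.32 | 1.57 | 1.26 |
| 0.5 | 1.32 | 1.32 | 1.15 |
| 0.7 | 1.32 | 1.03 | 0.95 |
| 0.9 | 1.32 | 0.59 | 0.58 |

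Example at rho = 0.7: 1.325 × √(1 − 0.49) = 1.325 × 0.714 = 0.95 mm. In sample-size terms this equals 1/(1 − 0.49) = 1.96 times as many participants. A change score is worse than no baseline when rho is below 0.5, which is why the adjusted analysis is preferred.

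The selective loss cannot be sized, since the documents give no expected rate of narrow sites.

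**The case against.** The strongest defence is that Hypothesis-2 and Aim 2 compare groups, and participants are randomised. A comparison of follow-up values needs no baseline to be valid: tooth position adds variance and chance imbalance, not systematic bias. Nothing says that the week-8 reading is meant to serve Aim 2. Week 7 is the time of the second CBCT, the scans hold the full three-dimensional anatomy, and the synopsis lists osseous change over time. CBCT is therefore a natural reading for Aim 2. The Manual of Procedures, which was not available, may also hold technique detail.

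Most of this stands, and it rules out several stronger readings that a reader might infer:

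- **That the ridge claim cannot be tested at all.** The documents do not support this. A randomised comparison of the week-8 reading, with complete data, is unbiased; the cost is precision.
- **That the week-8 reading is in whole millimetres.** Rounding is stated only for 4.7.2 (defects) and 4.7.3 (wound margins). Even if it applied, an SD of 1 mm would become √(1 + 1/12) = 1.041 mm, and power for a 1 mm difference would fall only from 0.562 to 0.529.
- **That the plan subtracts the socket-wall distance from the ridge reading and could so report gain where there was loss.** No section proposes this subtraction, and 4.7.1 does not say whether its distance is an inner or an outer one. Any fixed offset from wall thickness would also have the same expected value in both randomised arms.

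What the defence does not reach is that CBCT is given explicit tasks and the ridge is not among them. The variable for a named hypothesis belongs in the protocol and analysis plan even if a manual describes the technique. The argument from randomisation also weakens if narrow sites leave before they are probed.

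**Conclusion.** The point holds as a gap in endpoint definition with practical consequences. Hypothesis-2 and Aim 2 have no like-for-like ridge variable. The one explicit ridge reading is unpaired, a week later than Aim 2 specifies, and open to loss that depends on the outcome itself. It supports a valid but imprecise comparison between arms and gives no estimate of ridge change.

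The size depends on assumptions. At SD 1 mm with 10 per group, the detectable difference is about 1.32 mm without a baseline and 0.95 mm with one at rho = 0.7. The gain is negligible if rho is near 0 and more than halves the figure at rho = 0.9 (0.58 mm). The selective loss adds to this by an unknown amount. The plan should be changed, because the scans that would close the gap are already scheduled.

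**What to change.** In Aim 2 and sections 5.0, 13.1 and 13.4:

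1. Define the ridge outcome as bucco-lingual width at fixed levels, and ridge height, measured at the same landmarks on the post-grafting and week-7 CBCT scans.
2. Compare the groups at week 7, adjusting for the post-grafting value. Use one value per participant, or a model that allows for up to four sites in the same mouth.
3. Include every site with a week-7 scan, including those later exited for a narrow ridge. Report by group any site without that scan.
4. Keep the probe readings as supportive data, and state that the 4.7.1 socket-wall distance is not the baseline for the week-8 ridge reading.
5. In 5.0, reconcile the description of the first scan, which appears both as an aid to initial treatment planning and as the post-grafting baseline.

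The cost is protocol wording and some extra measurement on existing scans, preferably by a reader who does not know the assignment. No new visit or radiation exposure is needed.

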6.2 Implant Selection

The diameter and length of the implant will be determined by the surgeon based on the tooth location, anatomy, and bone volume determined from the CT scan prior to placement.

6.3 Drilling & Biopsy Technique

A standard drilling technique will be utilized except for a modification in the depth of the osteotomy and biopsy obtained from study sites described below. Copious amounts of sterile irrigant will be used in the osseous drilling procedure to prevent heating and thermal necrosis of the bone and surrounding tissue. The drill speed may be adjusted up to a maximum of 1500 rpm during the procedure. Thread forming or taping may be indicated in very dense bone and should be at a maximum of 30 rpm.

The surgeon will start with the 2mm diameter trephine drill for study sites and then proceed to increase the width with progressive depth drill depending on the implant diameter to be used at the site. The trephine with bone contained within will be harvested from the center core of one study site, per patient and will be immediately placed in fixative for later histological analysis. Vials will be labeled

with the participant's ID and the date of biopsy; laboratory technicians will be blinded to knowledge of participant group assignment.

6.4 Implant Placement

The sterile blister pack containing the implant will drop onto a sterile field and after thorough irrigation of the site the implant will be inserted directly into the prepared bone site. After implant placement the insertion torque will be measured with a torque wrench and recorded on the case report forms. A cover cap will be placed on the implant and the surgical wound sutured.

6.5 Immediate Post-Operative Procedures

Standardized intra-oral periapical dental radiographs will be made of each study site. Written and verbal post-operative instruction will be provided to each participant. An antimicrobial mouth rinse and ice packs will be dispensed. Antibiotics will be prescribed for 7 days; analgesics will be prescribed on an as needed basis at the discretion of the surgeon.

6.6 Implants Exposed

Implants will be exposed upon the investigator's determination that the implants are sufficiently integrated to withstand the forces of loading. In general, mandibular implants will be uncovered and restoration initiated approximately 4 months after placement; maxillary implants will be uncovered and restoration initiated approximately 6 months after placement.

Prior to exposing the implants subjects will be given a loading dose of antibiotics based on their medical history and concomitant medications. Local anesthesia will be achieved in the region by regional block or local infiltration. Conscious sedation may be added at the surgeon's discretion to help manage a patient's anxiety. The facial area will be scrubbed by 2% Chlorhexidine soap and the oral cavity disinfected by rinsing for 1 minute with a 0.12% chlorhexidine gluconate antimicrobial oral rinse prior to the procedure.

Once the treatment areas are sufficiently anesthetized a crestal incision will be made to reveal the top of the implant and an abutment will be attached. The incision will be closed with sutures and the temporary prostheses will be adjusted. Clinical photographs will be taken before, during and after the procedure; following the procedure and standardized intra-oral radiographic images of each implant site will be captured.

6.7 Post-Surgical Evaluation

Participants will return to clinic for oral evaluations approximately 14 days post-surgery; sutures will be removed at the 14-day visit. At this visit, medical history will be reviewed and any changes documented. Subjects will be referred to the prosthodontic investigators for restoration of the implants.

7.0 PERMANENT RESTORATION OF IMPLANTS

Implant restoration will be completed according to the prosthetic guidelines. Each implant will be restored in the conventional manner with an aesthetically pleasing single crown restoration. The restoring dentist will select restoring materials based on his discretion and the individual patient needs. Prosthetic restoration of the implants will require numerous visits to the restorative dentist over a

period of one to two months. The restoring dentist will advise when additional visits are necessary. Photographs and radiographs will be taken of each area when the final restoration is cemented.

8.0 LONGITUDINAL FOLLOW-UP

Post-Restoration Follow-up Evaluations (12-months and 24-months after the implant is restored)

Participants will return to the clinic at 12 and 24 months following permanent implant restoration. Evaluation of implant function and surrounding tissue health will be determined based on an interview with the participant, clinical examination of the study sites and an analysis of radiographic and photographic data.

At each visit, study personnel will review and update the participant's health history and record any adverse experiences; a study dentist will complete a thorough periodontal evaluation of the implant area and provide an assessment of the prosthetic attachment interface. A set of standardized periapical radiographs and clinical photographs will be made.

Case report forms will be used to record the following observations for each implant site:

- Overall soft tissue health
- Plaque and gingivitis scores (modified Löe and Sillness)
- Pocket depth and clinical attachment level
- Implant Stability
- Retention and stability of prosthetic attachment
- Overall aesthetics (soft tissue contours)
- Assessment of reported pain
- Implant survival

9.0 RADIOGRAPHIC AND PHOTOGRAPHIC SURVEYS

9.1 Intra-oral Radiographic Images

Standardized intra-oral periapical digital radiographic images will be obtained of each site prior to implant placement, when the implants are placed, when the implant is exposed, at permanent implant restoration and at twelve and twenty-four months after the implants are restored. A minimum of six images per study site over the duration of the study will be obtained. Additional images may be obtained based on the study dentist's determination of need.

Radiographic images will be used to monitor osseous health at the bone-implant interface, to verify implant position, to assess the quality of implant-attachment interface and to capture measurements of longitudinal osseous support to the implants. Consistently careful technique will yield images with similar geometry and with constant density leading to a valid and dependable analysis.

9.2 Radiographic Image Acquisitions

Longitudinal measurement of osseous support to the implant sites is reliant upon serial images of consistently similar quality that accurately image existing anatomy with minimal distortion over time. Ideal images for this study will center the targeted sites with at least 2mm of adjacent anatomy visible on each side of the implant.

9.3 Standardized Radiography

During this study, ensuring parallelism and standardization of periapical radiographs for measurement of osseous support will rely on consistent use of a Rinn bite-block and aiming ring and careful positioning of sensor in the oral cavity.

Thermoplastic impression tabs will be used to acquire an impression of the adjacent teeth in the area of interest, the impression will be attached to a Rinn bite-block; this will enable accurate positioning of the film during sequential exposures. After the initial exposure, the bite-block-impression will be disinfected, labeled with the subject ID and tooth number, and stored until needed for future exposures. Images will be acquired through the sequence of events listed below:

- 9.3.1 Select the area of interest
- 9.3.2 Assemble the needed materials
- 9.3.3 Prepare the thermoplastic tabs in a warm water bath according to package direction
- 9.3.4 Attach tabs to the bite block, insert the sensor and attach the Rinn aiming-ring apparatus
- 9.3.5 Position bite block/sensor in the oral cavity
- 9.3.6 Align the X-ray machine tube and flush against the aiming ring
- 9.3.7 Expose the image
- 9.3.8 Review the image for accurate positioning and quality
- 9.3.9 Label the image with subject ID and tooth number and save to a JPEG file for future use.
- 9.3.10 Disinfect the bite-block, label with subject ID and tooth number, and store for future use

As commonly practiced in the dental setting, participants will be draped with a protective apron with an attached thyroid collar while the radiographic images are captured. Dental X-ray equipment used in this trial is routinely inspected by the Department of Public Health. Only well-trained, qualified personnel will operate the imaging systems.

9.4 Clinical Photography

Each study site will be monitored with digital photography to assess the soft tissue healing. Photographic assessment will be based on images taken at 1:1 ratio with a Nikon D-7000 digital camera. Buccal and occlusal views will be obtained at the initial visit (prior to extraction), after completion of the grafting procedures, at 2 and 4 weeks, immediately prior to biopsy at 8-weeks, after implant insertion, at each prosthetic restorative visit, when the final restoration is attached and at four semi-annual follow-up visits.

